2.3.1 Data Conventions Limited to Diary data

- Study baseline diary information refers to the baseline information collected at the start of study 191622-120 (see Section 2.2).
- For study baseline and post-treatment visits, analyses will be based on the diary data collected over two consecutive days. For each day, the bladder diary will be used to collect date, time, and type of voiding episode (urinary incontinence, catheterization, or voluntary void) for each daytime episode (time between waking up to start the day and going to bed to sleep for the night). Furthermore, volume of urine on catheterization at morning wakening, the time the patient went to bed to sleep at night and the time the patient woke up in the morning and presence/absence of night time urinary incontinence will be collected for each diary day.

- The visit windows defined in Section 2.2 will be used to derive a patient's diary parameters for each visit.
- A valid diary day is defined as a day where there are one or more urinary episodes of any type (incontinence, catheterization, or voluntary void) during the daytime collection period. In the case of patients who provide just one valid diary day within a visit window, the 2-day frequency of daytime urinary incontinence will be prorated with the value from the valid diary day.
- If there are no valid diary days within the window, the 2-day diary data will be set as missing for the visit.
- For baseline and post-treatment visits, the 2-day diary will be determined based on the following algorithm:
 - 1) Apply visit windows defined in Section 2.2, which are based on days from the date of study drug injection.
 - 2) Determine the time of the first daytime urinary episode that is within the visit window (in the example below, 8:30 am on May 4). Count forward two consecutive daytime diary collection days. Note: the second daytime period should end within the window, i.e., prior to or on the last day specified in the window definition; otherwise, the nighttime or daytime data will not be used for the corresponding window. For baseline diary data, any urinary episode collected up to the time of injection will be counted towards the baseline diary data.
 - am on May 4 and ends with a bedtime of 11:00 pm (going to bed to sleep for the night). The bedtime for May 4 starts at 11:00 pm and ends at the wake time of 12:00 pm on May 5. The second daytime period starts on 12:00 pm on May 5 (wake time) and ends at 1:00 am May 6. Note that the wake time and bedtime can go over two calendar days. In the data set, for a given daytime, even if the daytime period goes over two calendar dates it will be recorded under the same calendar date (i.e., if the patient goes to bed for the night after midnight). The time of the day will be used to accurately attribute the date of the event.

- If there is a missing daily average frequency of episodes of daytime urinary incontinence at study baseline, the imputed values from study 191622-120 will be utilized (see the analysis plan for study 191622-120).
- The daily frequency of daytime urinary incontinence episodes will be normalized to a 12-hour daytime period. The following normalization algorithm will be used:
 - 1) Apply visit window defined in Section 2.2 which uses days from treatment as reference.
 - 2) Identify wake time and bedtime within the visit window. Daytime period (in hours) is determined by time between wake time and bedtime for that day.
 - 3) Using the example below, 4 urinary incontinence episodes are recorded during the first daytime period of 16 hours (7:00am to 11:00pm), and 7 episodes recorded during the second daytime period of 14 hours (8:30am to 10:30pm).

On a given day, the number of daytime urinary incontinence episodes normalized to a 12-hour daytime period will be calculated by

$$\frac{12}{\text{daytime period}}$$
 × number of daytime urinary incontinence episodes,

which, in the example, adjusts to 3 (= $(12/16) \times 4$) and 6 (= $(12/14) \times 7$) normalized urinary incontinence episodes, respectively. The daily average frequency of daytime urinary incontinence episodes by the normalized daytime period in a given visit window will be 4.5 (= (3 + 6)/2) in this example.

• If wake time is missing, the missing wake time will be imputed by the first morning catheterization where urine volume is collected. If both the wake time and the first morning catheterization are missing then the morning wake time will be imputed by either the first urinary episode time of any type recorded on that day or 7:00 am, whichever comes earlier. If bedtime is missing, the missing time will be imputed by either the last urinary episode time of any type recorded on that day or 10:00 pm, whichever comes later.

3. Disposition and Exit Status

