2.3 Data Conventions

The following data conventions will be applied to all analyses.

- Baseline and study baseline are used interchangeably throughout this document. They both refer to baseline information collected at the start of study 191622-120.
- In general, metric systems will be used (e.g., kilograms (kg) and centimeters (cm)) and clinical laboratory data will be presented with the Standard International (SI) units.
- The variance for Kaplan-Meier estimates will be calculated using Greenwood's formula.

- Descriptive statistics for continuous variables include the sample size (n), mean, SD, median, minimum (min), first quartile (Q1), third quartile (Q3), and maximum (max).
- Summary statistics for categorical variables include the sample size (n), frequency count and percent.
- The Medical Dictionary for Regulatory Activities (MedDRA) dictionary will be used to code all adverse events (AEs) and medical histories.
- World Health Organization Drug Dictionary Enhanced (WHO DDE) preferred name and MedDRA will be used to code all medications.
- Cumulative study duration from Day 1 (first injection date in preceding study 191622-120) will be calculated as:

Study day in study = visit date - day 1 date + 1.

 Cycle duration for a given Treatment X (i.e., Xth injection cycle where X > 1)will be calculated as:

Study day of cycle X = visit date - day 1 of Treatment X + 1.

- The algorithm presented in Table 3, together with the rules below will be used to impute incomplete or missing dates for adverse events and medications as follows:
 - (a) AE start dates will be imputed as the minimum of the following:
 - initial imputed date, where target date = first study drug injection date if the AE started in study 191622-120; exit day in study 191622-120 if the AE started in study 191622-121.
 - complete end date
 - (b) Medication start dates will be imputed as the minimum of the following:
 - initial imputed date, where target date = first study drug injection date 1 if the medication started in study 191622-120; exit day in study 191622-120 if the medication started in sudy 191622-121.
 - complete end date
 - (c) AE and Medication end dates will be imputed as the minimum of the following:

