5.1 Collection of Key Efficacy Measurement and Derivation of Key Efficacy Variable

In this long-term extension study no primary or secondary efficacy variable has been defined. However, the key efficacy measure is the change from baseline to posttreatment in the normalized daily average frequency of daytime urinary incontinence episodes (daytime is defined as the time between waking up to start the day and going to bed to sleep for the

night). The daily average frequency of daytime urinary incontinence episodes is obtained using the total number of daytime urinary incontinence episodes recorded in a 2-day bladder diary divided by 2, and study baseline frequency is defined as the daily average frequency of episodes of daytime urinary incontinence preceding the study treatment in study 191622-120.

Each daytime period recorded in the bladder diary is normalized to represent a 12-hour period to account for differing durations of the daytime period (see Section 2.3 for further details). Furthermore, if there is just 1-day valid bladder diary data, this will be used as the daily average frequency of daytime urinary incontinence episodes (see Section 2.3 for further details).

The key time point for this change from baseline endpoint will be week 6 after each treatment/injection.

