5.2 Key Efficacy Analyses

Since there is no primary efficacy measure, this section describes the analysis for the key efficacy variable.

For each cycle, for each post-treatment visit, mean values and mean change from study baseline values for the daily average frequency of normalized daytime urinary incontinence episodes will be presented together with the associated t-distribution based 95% CIs for the mean change from study baseline. This summary will be presented for each BOTOX treatment group of that cycle. This summary will also be repeated for the non-normalized daily average frequency of daytime urinary incontinence episodes. The key timepoint for analysis for each cycle is week 6 posttreatment.

For patients that increased their BOTOX dose from 50 U to 100 U or from 100 U to 200 U a paired difference will be derived between the lower dose cycle and the subsequent higher dose cycle's week 6 daily average frequencies normalized daytime urinary incontinence episodes values. These values will be summarized using mean paired difference, associated standard error and paired t-test.

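### A partial injection day can enter the baseline diary with a full-day denominator, which makes that child's baseline too low in every cycle

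*SAP*

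**What the plan says.** SAP 2.3.1 starts at the first daytime entry in the visit window and counts forward two successive daytime periods. A Note adds that the second period must finish inside the window, or its data are left out for that window. A provision for baseline only follows directly: "For baseline diary data, any urinary episode collected up to the time of injection will be counted towards the baseline diary data".

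Normalisation comes later in the same section. Each day's count is multiplied by 12 over the length of the daytime period: "Daytime period (in hours) is determined by time between wake time and bedtime for that day". The injection day is not treated separately. On gaps, "If bedtime is missing, the missing time will be imputed by either the last urinary episode time of any type"; the alternative is 10:00 pm, and the later of the two is taken.

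On validity, "A valid diary day is defined as a day where there are one or more urinary episodes of any type", with no minimum number of observed hours. When only one day qualifies, "the 2-day frequency of daytime urinary incontinence will be prorated with the value from the valid diary day".

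On the terms baseline and study baseline, SAP 2.3 says: "They both refer to baseline information collected at the start of study 191622-120". SAP 5.2 states that for each cycle and post-treatment visit "mean values and mean change from study baseline values for the daily average frequency of normalized daytime urinary incontinence episodes will be presented". SAP 5.3.1 uses the same baseline for the 50%, 75%, 90% and 100% reduction thresholds.

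**The concern.** At baseline the numerator stops at the injection, but nothing in the text stops the denominator there. A diary that ends when the child goes to the procedure has no bedtime entry, so the imputation rule supplies an evening one. One catheterisation before the procedure makes the day valid, and it then carries the same weight as a complete day. The missing-baseline imputation offers no protection, because a partial day counts as valid, not missing.

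The baseline-only sentence has a real effect. Episodes on earlier complete days are already captured by the two-day count, so what it adds is the injection day, the one day the normalisation does not handle.

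Each child has one baseline, reused at every visit of every cycle. A value that is too low therefore reduces the recorded improvement throughout follow-up and can turn a responder into a non-responder. It also enters the baseline summary in SAP 4.2.

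**Working it through.** **1. The plan's own example (SAP 2.3.1).** Day 1 has 4 episodes in 16 h and day 2 has 7 episodes in 14 h (8:30 am to 10:30 pm).

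- Day 1: (12/16) × 4 = 3
- Day 2: (12/14) × 7 = 6
- Average: (3 + 6)/2 = 4.5, as the SAP states.

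**2. The same example with day 2 as the injection day.** Assumptions: day 2 has a constant rate of 7/14 = 0.5 episodes per hour, and the injection time varies. Literal day-2 score = (12/14) × 0.5 × hours from 8:30 am to injection.

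| Injection | Hours | Day-2 score | Baseline | Error against 4.5 |
|---|---|---|---|---|
| 9:30 am | 1 | 0.43 | 1.71 | -62% |
| 10:30 am | 2 | 0.86 | 1.93 | -57% |
| 12:30 pm | 4 | 1.71 | 2.36 | -48% |
| 3:30 pm | 7 | 3.00 | 3.00 | -33% |
| 6:30 pm | 10 | 4.29 | 3.64 | -19% |

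If the denominator ends at injection, day 2 scores (12/h) × 0.5h = 6 in every row and the baseline returns to 4.5. At 12:30 pm with bedtime missing and set to 10:00 pm, the day scores (12/13.5) × 2 = 1.78 and the baseline is 2.39, so imputation does not help. The non-normalised value is also low: (4 + 2)/2 = 3.0 instead of (4 + 7)/2 = 5.5.

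**3. General form.** Let f be the fraction of the waking day before injection, with the same constant rate on both days. The injection day is scored at f times its true value, so the baseline is multiplied by k = (1 + f)/2, or by k = f if it is the only valid day. A true reduction r is recorded as 1 - (1 - r)/k.

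| f | k, two days | True 50% recorded as | True 75% recorded as |
|---|---|---|---|
| 0.10 | 0.55 | 9% | 55% |
| 0.25 | 0.625 | 20% | 60% |
| 0.50 | 0.75 | 33% | 67% |
| 0.75 | 0.875 | 43% | 71% |

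With r = 100% the formula returns 100% for any k above zero. The 100% threshold therefore moves only if the baseline itself is scored as zero; the 50%, 75% and 90% thresholds are exposed.

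**4. One illustrative record.** Assumed: 4 episodes per 15-hour day (6:30 to 21:30), injection at 10:00 on the second diary day, and 1 episode before it.

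- Full day: (12/15) × 4 = 3.2
- Injection day as written: (12/15) × 1 = 0.8
- Baseline: (3.2 + 0.8)/2 = 2.0, and 2.0/3.2 - 1 = -37.5%
- Expected rather than whole-number count: f = 3.5/15 = 0.233, k = 0.617, baseline 1.97 (-38%). With 2 to 5 pre-injection hours the error runs from -43% to -33%.
- Assumed week 6 value of 1.5: true reduction 1 - 1.5/3.2 = 53%; recorded reduction 1 - 1.5/2.0 = 25%.

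**The case against.** The strongest reply is that the full-day denominator on the injection day is inferred. Normalisation uses wake time and bedtime inside the visit window. If the baseline window closes at injection and the Note applies, the injection day drops out, the one-valid-day rule uses the day before, and the record above gives the correct 3.2. This reading is possible but not secure. The baseline sentence follows the Note and reads naturally as an exception to it, and the 10:00 pm rule supplies a long denominator. The limits of the baseline window, which would settle it, are not in the available text, and that absence cannot be held against the plan. The study 191622-120 plan, which may deal with the partial day, is not available either.

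A second reply is that few children may be affected. Protocol 7.2 places the diary on 2 consecutive days in the week before a visit, and the algorithm counts forward from the first entry. The injection day matters only if it is among the first two diary days or is the only valid one. This stands, and it prevents any estimate of a shift in the group mean.

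A reader might also infer that the sentence adds injection-day episodes to two complete days, giving a baseline that is too high and creating response. The documents do not support this. The algorithm counts two daytime periods, and SAP 5.1 derives the average "using the total number of daytime urinary incontinence episodes recorded in a 2-day bladder diary divided by 2".

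Finally, the study is uncontrolled and descriptive (Protocol 5.2 and 7.3), so no test is at risk, and the error understates benefit.

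**Conclusion.** The point holds in a limited form. SAP 2.3.1 allows a partial injection day to be scored as a full baseline day, and two programmers could follow the text to different baselines. For an affected child with equal rates on both days, the two-day baseline is multiplied by (1 + f)/2; in the illustrative record it is 2.0 instead of 3.2. Change from baseline and the 50%, 75% and 90% responder results are then understated for that child in every cycle, including the first.

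This rests on three conditions: the injection day is used as a diary day, the window Note does not remove it, and the episode rate is roughly constant over the day. The week 6 value of 1.5 was chosen to lie just on the responder side of 50%; it shows that reclassification can happen, not how often.

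A reader might go further and conclude that the study's reported efficacy is biased. The documents do not support that: they give no count of affected children and do not show the baseline window. The paired dose-increase comparison in SAP 5.2 is untouched, because it uses week 6 values only.

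**What to change.** Keep the existing selection of two diary days and add one rule to SAP 2.3.1, in either of two forms:

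- **Preferred:** a partial injection day is not a valid baseline diary day. The one-valid-day rule then covers a child left with one day, and the existing missing-baseline provision covers a child left with none.
- **Alternative:** end that day's daytime period at the injection time in the 12-hour normalisation, with a minimum number of observed hours. This is correct on average under a constant rate but unstable over short periods. In the record above, one episode in 3.5 h scores (12/3.5) × 1 = 3.43, and two would score 6.86.

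Treat the non-normalised value consistently, since dividing a partial day as a full one biases it in the same way. Match the derivation to the study 191622-120 plan so that each child has one baseline across both studies; if that plan already settles the injection day, a cross-reference is enough. Before lock, list the children whose baseline diary uses the injection day, so that the extent is known.

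The cost is a sentence or two in the SAP, a small programming change and a check against study 191622-120, with no new data. The downside is a slightly noisier one-day baseline for a few children.

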3.1 Screening Log Data

Not applicable.

3.2 Disposition and Exit Status

For study 191622-121, patient disposition table will be produced by cycle and for the study overall. The overall study disposition summary table will display summary by what the patients received in Cycle 1 (safety treatment groups in Study 191622-120) and for the

overall BOTOX-treated population. For the by cycle tables, summaries will be presented by the BOTOX treatment received in the given cycle. A listing of patients' disposition information will also be generated.

3.3 Study Duration

See Section 6.1.1.

3.4 Protocol Deviations

Significant and non-significant deviations are defined in the Protocol Deviations Specification Document and will be determined prior to database lock. A by patient protocol deviation listing and table will be produced for these significant protocol deviations. The protocol deviation table will be presented by Cycle 1 treatment groups (safety treatment groups in Study 191622-120) and for the overall BOTOX-treated group. Furthermore, the deviation listing will present the deviation type and detail.

4. Demographics and Other Baseline Characteristics

Baseline assessments are defined to be assessments taken prior to first BOTOX injection received in study 191622-120.

4.1 Demographics

Age, race, sex, weight (kg) and height (cm) will be summarized for the overall BOTOX-treated group and by Cycle 1 treatment groups. Race will be summarized as Caucasian, Black, Asian, Hispanic, and Other.

4.2 Disease Characteristics

The following baseline information will be summarized for the overall BOTOX-treated group and by Cycle 1 treatment groups:

- study baseline information on stratification factors (age $< 12 \text{ vs} \ge 12 \text{ years}$; daytime urinary incontinence $\le 6 \text{ vs.} > 6$ episodes over the 2-day diary collection period),
- baseline bladder characteristics (presence or absence of open bladder neck, external sphincter dyssynergia, fecal incontinence, bladder sensation with filling, and whether or not the patient is ambulatory),
- baseline bladder wall thickness
- use of anticholinergic therapy at baseline (on day of injection),

- number of prior anticholinergic therapy used for urinary incontinence
- duration of prior anticholinergic therapy used for urinary incontinence
- reason prior anticholinergic therapy not considered to adequately managed urinary incontinence
- daily average frequency of normalized daytime urinary incontinence episodes,
- daily average urine volume at first morning catheterization (mL),
- presence/absence of night time urinary incontinence,
- number of urinary tract infection (UTI) within 6 months prior to screening. The
 number and percentage of patients that have 0, 1, 2, 3 and > 3 UTIs within 6-months
 of screening will also be summarized
- A patient's neurological characteristics (spinal dysraphism, spinal cord injury or transverse myelitis), and
- urodynamic assessments namely, presence or absence of involuntary detrusor contraction (IDC), maximum cystometric capacity (MCC) (mL), maximum detrusor pressure during the first IDC (Pdet_{Max1stIDC}) (cm H₂O) if IDC present, maximum detrusor pressure (Pdet_{Max}) (cm H₂O) during the storage phase, and detrusor leak point pressure (DLPP) (cm H₂O).

4.3 Prior Medications

Prior medications are defined as any medications which are administered prior to the first BOTOX injection. Prior medications will be summarized for the overall BOTOX-treated group and by Cycle 1 treatment groups.

4.3.1 Prior Anticholinergic Medications for Urinary Incontinence

The number and percentage of participants with prior anticholinergic medications for urinary incontinence will be summarized by WHO Drug Class and WHO DDE preferred drug name.

4.3.2 Antibiotic Medication for Prophylactic Treatment

All prophylactic antibiotic medication associated with study drug treatment will be summarized by WHO Drug Class and WHO DDE preferred drug name. The summary will be presented by treatment cycle.

4.4 Concomitant Medications/Procedures

A concomitant medication is any medication which is administered any time after the first BOTOX injection.

4.4.1 Concomitant Anticholinergic Medications for Urinary Incontinence

Concomitant anticholinergic medication for urinary incontinence will be summarized by WHO Drug Class and WHO DDE preferred drug name as described for the prior medication for the overall BOTOX-treatment group and by Cycle 1 treatment groups.

4.4.2 Concomitant Medication

Concomitant medications will be summarized by WHO Drug Class and WHO DDE preferred drug name as described for the concomitant anticholinergic medication for the overall BOTOX-treatment group and by Cycle 1 treatment groups.

4.4.3 Concurrent Procedures

A patient listing of concurrent procedures will be produced. This listing will include information on the BOTOX cycle and BOTOX dose received.

4.5 Past Medical History

Medical history information will be coded with the MedDRA dictionary. Frequencies and percentages will be summarized by MedDRA primary System Organ Class (SOC) and preferred term for the overall BOTOX treated group and by Cycle 1 treatment groups.

5. Efficacy Analyses

All efficacy analyses will be by treatment cycle and by treatment received at each cycle, for the BOTOX treated population. The key timepoint for each efficacy variable and cycle is 6 weeks post treatment.

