# 5.5 Method for Assignment to Treatment Groups/Randomization

There will be no randomization in this long-term extension study.

All patients who receive treatment in this study will receive BOTOX. The blinded dose received (50, 100, or 200 U BOTOX, not exceeding 6 U/kg) will be dependent on the assessment of the clinical response (efficacy and safety) to the previous blinded study treatment (which will have been 50, 100, or 200 U BOTOX, not exceeding 6 U/kg). The patient/parent/caregiver will be questioned on their treatment response to establish if, in their opinion, the current treatment response is adequate or if there was little or no treatment benefit and whether they would be willing/want to have a higher dose. They will also be questioned on whether the patient is experiencing side effects. Using this information, the investigator will use his/her own clinical assessment of the patient and apply the following criteria for the retreatment dose request:

- if the benefit/risk balance is evaluated by the investigator to be appropriate at the current dose, then the same dose would be requested
- if the investigator assessed that, although the preceding dose was well tolerated, the
  response received was insufficient and warrants a higher dose, then a dose increase would
  be requested

• if the investigator assessed that there were side effects that would warrant a lower dose, the patient would be exited from the study

Compared to the previous treatment, the investigator therefore has the following options:

- elect to keep the same dose as received at the previous treatment (not to exceed 6 U/kg)
- elect to increase the dose compared to the previous treatment (not to exceed 6 U/kg):
- if the patient received 50 U BOTOX at the previous treatment, they would receive 100 U BOTOX
  - if the patient received 100 U BOTOX at the previous treatment, they would receive 200 U BOTOX
  - if the patient received 200 U BOTOX at the previous treatment, they would remain at 200 U BOTOX (after 2 requests to increase the dose from 200 U the patient will be exited; see below)

At the qualification for retreatment visit the investigator or designee will contact the IVRS/IWRS and indicate the treatment option for the patient. IVRS/IWRS options will be either to remain at the same dose or to increase the dose since patients will be exited from the study if the investigator assessed that a lower dose was warranted (see below).

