#### 5.9 Treatment Administration

# 5.9.1 Day of Treatment Criteria

Treatment will be administered within 4 weeks of qualification for retreatment (see Section 5.10.1 for qualification for retreatment criteria), but no later than 48 weeks since study enrollment on day 1 of this study. The following "day of treatment criteria" must be fulfilled prior to each administration of study medication:

- patient does not have a UTI, in the opinion of the investigator (taking into account patient symptoms, presence of significant leukocyturia at screening (e.g. ≥ 30 WBC/HPF), urine culture results, need for antibiotic treatment,etc)
- appropriate prophylactic antibiotics have been initiated (see Section 5.9.2)
- antiplatelet or anticoagulant therapy or medications with anticoagulative effects have been discontinued at least 3 days prior to treatment
- negative urine pregnancy result (for postmenarche females)
- investigator continues to deem treatment is appropriate and no condition or situation exists which, in the investigators opinion, puts the patient at significant risk from receiving retreatment

Note: If a patient does not fulfill the "day of treatment criteria", they would still be considered qualified for retreatment (ie, qualification for retreatment or any associated procedures are not to be repeated). The treatment administration visit would be rescheduled for as soon as possible (if applicable), and the day of treatment criteria would need to be fulfilled prior to treatment administration.

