### 7.3.1 Efficacy Analyses

The efficacy analysis will be based on the BOTOX-treated population. Week 6 after each treatment will be the timepoint of main interest and the efficacy variable of key focus is change from baseline in the daily average frequency of daytime urinary incontinence episodes. Data will be presented by BOTOX treatment cycle according to the dose received at that treatment cycle (grouped to the nearest dose group, ie, 50, 100 or 200 U BOTOX), as well as by an overall BOTOX group (ie, regardless of dose).

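### The by-cycle, by-dose efficacy tables mix change in effect with change in who is treated and at what dose, and no planned table follows the same patients across cycles

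*SAP*

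**What the plan says.** - **Analysis structure.** SAP Section 5: "All efficacy analyses will be by treatment cycle and by treatment received at each cycle". For the key variable, week-6 change in normalized daytime incontinence episodes, SAP 5.2 adds: "This summary will be presented for each BOTOX treatment group of that cycle". SAP 5.3.1 uses the same layout for the responder percentages. Protocol 7.3.1 also asks for a pooled row, "as well as by an overall BOTOX group (ie, regardless of dose"), which SAP 5.2 does not mention.
- **Baseline.** One fixed baseline serves every cycle. On the terms baseline and study baseline, SAP 2.3 says: "They both refer to baseline information collected at the start of study 191622-120".
- **Reaching a further cycle.** Protocol 5.10.1 requires a request, at least 2 daytime episodes over the 2-day diary, at least 12 weeks since the last treatment and no serious treatment-related adverse event. Protocol 5.9.1 requires treatment "no later than 48 weeks since study enrollment on day 1 of this study".
- **Dose.** Protocol 5.5 lets the investigator request one level more if the previous dose was tolerated but the "response received was insufficient and warrants a higher dose". A second such request in a patient already at 200 U leads to exit.
- **Within-patient efficacy contrast.** SAP 5.2 has one, limited to patients whose dose was raised: "a paired difference will be derived between the lower dose cycle and the subsequent higher dose" cycle.

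**The concern.** Protocol Section 1 gives the purpose of the extension as evaluating long-term data over repeated treatments, and describes the adult programme as showing similar reductions from one treatment to the next. Readers will look for the same pattern here by reading down the cycle means.

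Those means come from different sets of patients. Later cycles hold patients whose symptoms returned sooner. Within a cycle, the dose rows are sorted by earlier response: patients who did well stay at the low dose, and patients who did poorly move up. A row can therefore drift although no patient's response changes. Showing n for each cell tells the reader that the set has shrunk, but does not correct the mean.

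At stake is the interpretation of durability. No test or error rate is affected.

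**Working it through.** **1. The plan's own figures.** The maximum duration reproduces: 48 + 12 = 60 weeks. The expected number entering is about 100 in the protocol and about 78 in the SAP, both at 76% rollover. The number randomized in the preceding study is not given, so neither can be reproduced (100/0.76 = 132; 78/0.76 = 103). Both are carried below. No per-cycle number is stated.

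**2. Who can reach each cycle (from the rules alone).** Cycle 1 is in the preceding study. The earliest cycle 2 is at day 1 of the extension. Cycle k (k ≥ 3) then needs k - 2 further injection-to-injection intervals inside 48 weeks, so the mean interval is at most 48/(k - 2).

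- Cycle 2: open up to about 48 + 48 = 96 weeks after the first injection, so almost no selection on duration.
- Cycle 3: one interval of at most 48/1 = 48 weeks.
- Cycle 4: mean at most 48/2 = 24 weeks.
- Cycle 5: mean at most 48/3 = 16 weeks.
- Cycle 6: 48/4 = 12 weeks, exactly the minimum interval.
- Cycle 7: 5 × 12 = 60 > 48, impossible.

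**3. What the tables show when nothing changes.** Monte Carlo, 200,000 to 400,000 patients, with each patient's true week-6 change constant over cycles. Inputs assumed, not in the documents: mean change -1.3 episodes/day, between-patient SD 1.0, within-patient SD 0.8; log-normal duration with median 30 weeks, between-patient log-SD 0.5 and within-patient log-SD 0.2; 2 weeks from qualification to treatment; equal thirds per dose in cycle 1; a dose increase requested when the observed reduction is below 0.65/day. Rho is the correlation between size of benefit and duration. From the documents: the 12-week minimum, the 48-week limit, one-level increases and the exit rule at 200 U.

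Share reaching cycles 2/3/4/5, without dose changes: 98/74/24/5%. With median duration 20 weeks, 92% and 53% reach cycles 3 and 4; with 40 weeks, 54% and 10%.

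Mean change in cycles 1 to 4:

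| Scenario (true effect constant) | Row | C1 | C2 | C3 | C4 |
|---|---|---|---|---|---|
| No dose change, rho 0 | pooled | -1.30 | -1.30 | -1.30 | -1.30 |
| No dose change, rho 0.3 | pooled | -1.30 | -1.29 | -1.18 | -0.93 |
| No dose change, rho 0.6 | pooled | -1.30 | -1.28 | -1.05 | -0.55 |
| No dose change, rho -0.3 | pooled | -1.30 | -1.31 | -1.42 | -1.67 |
| Increase and exit, no dose effect, rho 0 | pooled | -1.30 | -1.30 | -1.38 | -1.49 |
| Increase and exit, no dose effect, rho 0.3 | pooled | -1.30 | -1.29 | -1.26 | -1.17 |
| Increase and exit, 0.5/day per level, rho 0.3 | pooled | -1.30 | -1.39 | -1.46 | -1.42 |
| Increase and exit, no dose effect, rho 0.3 | 50 U | -1.30 | -1.68 | -1.80 | -1.79 |
| Increase and exit, no dose effect, rho 0.3 | 200 U | -1.29 | -1.08 | -0.95 | -0.87 |

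The last two rows have the layout SAP 5.2 specifies. The 50 U row shows a false gain of 0.49/1.30 = 38% and the 200 U row a false loss of 0.42/1.29 = 33%. Most of the 50 U drift and about half of the 200 U drift is already there at cycle 2, which 98% reach. It comes from response-driven dosing, not from the 48-week limit.

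**4. Does following the same patients help?** At rho 0.3:

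- No dose change, cohort reaching cycle 4: -0.93 in all four cycles. Flat, as it should be.
- Increase and exit, no dose effect: -1.22, -1.22, -1.22, -1.17. Nearly flat.
- Increase and exit, 0.5/day per level: -1.17, -1.32, -1.42, -1.42. The improvement is the dose increase, not repetition, so dose must be visible.
- Only patients reaching cycle 3 on an unchanged dose, under the increase and exit rules: -1.81, -1.81, -1.66. A false decline, because staying on a dose selects on response in cycles 1 and 2 and cycle 3 regresses to the mean.

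**5. Precision of the difference from cycle 1.** SD of the difference = 0.8 × √2 = 1.13. Half-width = t × 1.13/√n, using the shares without dose changes.

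- At least 2 injections (98%): n = 76 to 98, ±0.26 to ±0.23.
- At least 3 (74%): n = 58 to 74, ±0.30 to ±0.26.
- At least 4 (24%): n = 19 to 24, ±0.55 to ±0.48.

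**The case against.** The strongest reply is that the study is descriptive. Protocol 7.3 rules out hypothesis testing and SAP 5.1 names no primary or secondary efficacy variable, so no decision depends on a cycle trend. Readers also get disposition by cycle and dose (SAP 3.2), Kaplan-Meier duration by cycle and dose, and per-patient average durations by dose (SAP 5.3.4). This stands as a limit on severity. It does not remove the point: disposition shows attrition without adjusting for it, and the per-patient averages pool over cycles, so they say nothing about trend. The SAP accepts a related principle for safety. SAP 6.2 adds a day-84 adverse event summary because time in cycle varies, but efficacy has no counterpart for changing patient mix.

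A reader might infer more: that only short-duration patients reach later cycles, so a constant effect will look like waning. The documents do not support that. Cycle 2 is open to almost everyone and cycle 3 allows an interval of up to 48 weeks. A false pooled loss from selection on duration needs shorter duration to go with smaller benefit. That is plausible, but no figure for it is given; at rho 0 without dose changes there is no trend, and at -0.3 there is a false gain. The increase and exit rules then shrink or reverse the pooled trend.

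It is also fair that a same-patient table is not clean. It mixes dose increase with repetition, and the cohort with at least 4 injections is small. Such a table should be supportive, not the sole basis for conclusions.

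**Conclusion.** The point holds as confounding of unknown pooled direction. Comparisons between cycles in SAP 5.2 and 5.3.1 are confounded by who reaches each cycle (clearly from cycle 4, weakly at cycle 3, hardly at cycle 2) and by response-driven dose increase and exit (from cycle 2 on). The reachability limits follow from the protocol's rules alone.

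The sizes do not. False drifts of about 38% at 50 U and 33% at 200 U by cycle 4, and pooled cycle-4 values anywhere from -0.55 to -1.67 against a cycle-1 mean of -1.30, all rest on assumed effect sizes, durations and correlations. They show that the tables can mislead in either direction. They do not predict what this trial will show. No single percentage of false loss can be stated for it.

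Because the study is descriptive, this is a cheap improvement to interpretation.

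**What to change.** Add to SAP 5.2 and 5.3.1 a supportive same-patient table:

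- Cohorts: patients with at least 2, at least 3 and at least 4 injections.
- Content: week-6 change and 50% responder rate in every cycle, and the within-patient difference from cycle 1 with 95% CI.
- Dose: the distribution in each cycle, with patients who had a dose increase marked, so that a change of dose is not read as an effect of repetition.
- An unchanged-dose version may be added but should not be the only one, because it selects on response.

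Add one sentence to SAP Section 5 saying that the by-cycle, by-dose means are not to be read alone as evidence of maintained or waning effect.

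The cost is one extra table set from data already collected, with no change to visits or treatment. The downside is imprecision in the smallest cohort: about 19 to 24 patients if 24% of 78 to 100 reach cycle 4. With median duration of 40 or 20 weeks, 10% to 53% would give about 8 to 53 patients.
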